5.2.2.1.1 Dose Specifications and Treatment Delivery

Radiotherapy will be delivered as 24 Gy over 3 fractions. There should be a minimum of 12 hours and a maximum of 96 hours between treatments. All treatments must be completed within week 1 – 2 of cycle 2. If a patient cannot receive a radiation fraction it will be skipped. The dose per fraction is to be prescribed such that 95% of the planning treatment volume (PTV) is encompassed by the prescription dose.

5.2.2.1.2 Technical Factors

Only photon (x-ray) beams with photon energies 4-15 MV or electron beams with electron energies of 6-12 MeV will be allowed.

5.2.2.1.3 Localization, Simulation, and Immobilization

Patients will be positioned in a stable position capable of allowing accurate reproducibility of the target position from treatment to treatment. Patient immobilization must be reliable enough to ensure that the gross tumor volume (GTV) does not deviate beyond the confines of the PTV as with any significant probability (i.e., <5%). Patients will undergo an imaging study (electron portal imaging, conebeam computed tomography or Megavoltage computed tomography)

immediately prior to treatment to ensure proper alignment of the geometric center (i.e., isocenter) of the simulated fields.

5.2.2.1.4 Target Volumes

Image Acquisition

Computed tomography will be used for targeting and treatment planning. IV contrast is encouraged when its use will enhance target delineation but is not required. Axial acquisitions with gantry 0 degrees will be required with spacing ≤ 3.0 mm between scans in the region of the tumor.

Target Volume

The treatment lesion will be outlined and designated the gross tumor volume (GTV). No additional clinical target volume (CTV) margin for microscopic spread will be added. Depending on the stability and reproducibility of patient setup an additional margin of 0.3 – 2 cm will be added to the GTV to constitute the PTV.

Organs at Risk

All organs at risk within axial slices containing the PTV and expected to be within the treatment field should be contoured. All standard normal tissue constraints for 3 fraction radiotherapy per RTOG guidelines should be observed. Treatment hotspots in radiosensitive organs should be avoided and the dose can be modified to respect normal tissue tolerance as outlined in section 5.4.2. The maximum point dose to 0.1cc should not exceed 25 Gy for skin (defined as outermost 0.5 cm rind on axial slices) and major peripheral nerves (i.e., brachial plexus, sacral plexus, sciatic etc.). The maximum point dose should not exceed 18 Gy to the spinal cord.

Technique and Dose Calculations

Conformal treatment approaches including 3D conformal radiotherapy using static, preferably non-coplanar fields; intensity modulated radiotherapy (IMRT), Volume Modulated Arc therapy (VMAT), Dynamic Conformal Arc Radiation Therapy (DCART), and helical tomotherapy are acceptable. Isodose lines covering the PTV must be $\geq 95\%$ of the prescribed dose. When IV and/or oral contrast are used, contrast densities should be overridden in the planning process. Tissue density heterogeneity correction is required for lung tumors. Superposition/convolution dose algorithms are preferred.

All radiotherapy plans will be centrally reviewed by the principal investigator or co-principal investigator prior to delivery of the first fraction.

5.2.2 Pembrolizumab

Pembrolizumab will be started during week 1 of Cycle 1 with cycles every 3 weeks.

5.2.2.2.1 Timing of Dose Administration

Pembrolizumab should be administered on Day 1 of each cycle after all procedures/assessments have been completed as detailed on the Study Calendar (Section 6.0). Pembrolizumab may be administered up to 3 days before or after the scheduled Day 1 of each cycle. Pembrolizumab will be administered on an outpatient basis. Pembrolizumab 200 mg will be administered as a

30-minute IV infusion every 3 weeks. Sites should make every effort to target infusion timing to be as close to 30 minutes as possible. However, given the variability of infusion pumps from site to site, a window of -5 minutes and +10 minutes is permitted (i.e., infusion time is 30 minutes: -5 min/+10 min).

Refer to section 10.2 for specific instructions for the preparation of the pembrolizumab infusion fluid and administration of infusion solution.

5.2.2.3 Interleukin-2

Interleukin-2 will be delivered into the treatment lesion by intralesional injections starting 24-96 hours after the completion of radiotherapy and to be completed during Cycle 2. Once needle is placed, intralesional IL-2 will be administered by qualified personnel. Intralesional IL-2 injections will follow guidelines, which we have previously published [46]. Briefly, each patient will receive an initial dose of 3×10^6 IU of IL-2, which will be escalated to 7×10^6 for the second treatment and then 15×10^6 IU for the final two treatments as tolerated. At dose escalation levels 2 and 3, each patient will receive a test of 3×10^6 IU for their first injection prior to escalation to higher doses according to our published guidelines. If a dose level is not tolerated (i.e., grade 3-4 non-hematologic toxicity) the treatment will be de-escalated to previous dose levels for subsequent treatments. If the initial dose of 3×10^6 IU of IL-2 is not tolerated the dose can be reduced to 1 million IU. Safety and toxicity will be evaluated using CTCAE v4.03. A dose limiting toxicity (DLT) will be defined as a treatment related grade 3-4 toxicity non-hematologic toxicity and will require dose de-escalation. If a DLT does not resolve within 5 days, is not responsive to management, or occurs at the lowest dose level (1 million IU IL-2) after de-escalation then that patient will be removed from trial and the therapy will be deemed intolerable. Therapy will be deemed safe and tolerable if no greater than 33% of patients find the treatment intolerable.

5.3 Monitoring

Safety will be evaluated in this study through the monitoring of all serious and non-serious AEs, defined and graded according to NCI CTCAE v4.03. Patients will be assessed for safety (including laboratory values) according to the Study Calendar. Patients will be followed for safety for 30 days following the last dose of study treatment when possible or until receipt of another anticancer therapy, whichever comes first.

Patients who have an ongoing study treatment-related AE upon study completion or at discontinuation from the study will be followed until the event has resolved to baseline grade, the event is assessed by the investigator as stable, new anticancer treatment is initiated, the patient is lost to follow-up, the patient withdraws consent, or until it has been determined that study treatment or participation is not the cause of the AE.

5.4 Dose Selection/Modification

5.4.1 Intralesional IL-2

5.4.1.1 Maximum Tolerated Dose Selection

In Phase I, four target doses of intralesional IL-2 will be evaluated:

- Dose Level -1: 1×10^6 IU;
- Dose Level 1: 3×10^6 IU;
- Dose Level 2: 7×10^6 IU;
- Dose Level 3: 15×10^6 IU (starting dose)

We will initiate the trial at Dose level 3 and de-escalate to lower dose levels as needed to establish the MTD. If dose level -1 is not tolerated the study will be halted and modified after discussion with principal investigators and study sponsors.

The MTD will be defined in phase I as the highest dose at which no more than one of six patients develops a DLT or Dose Level 3 if the MTD is not reached. A DLT is defined as one of the following which occurs during DLT period which lasts until 7 days after last injection of IL-2:

- grade ≥ 4 injection site reaction OR
- grade ≥ 3 treatment related immunologic adverse event (excluding injection site reactions) OR
- other grade ≥ 3 treatment related adverse events that do not resolve to grade ≤ 2 within 14 days OR
- AST/ALT $> 3 \times$ ULN with bilirubin $> 2 \times$ ULN, OR
- pneumonitis that requires holding treatment > 14 days

Table 4 and

Table 5 describe the standard dosing rules that will be followed. At dose levels 2 and 3 each patient will receive a test dose of 3×10^6 IU for their first injection prior to escalation to higher doses according to our published guidelines. For example, at dose level 3 each patient will receive an initial test dose of 3×10^6 IU of IL-2, which will be escalated to 7×10^6 for the second treatment and then 15×10^6 IU for the final two treatments as tolerated. If a dose level is not tolerated the treatment will be de-escalated to previous dose levels for subsequent treatments. Subjects who are not evaluable for toxicity will be replaced for DLT assessment. If subjects cannot receive 75% of intended dose of study treatment, for reasons other than toxicity and did not experience a DLT, they will be replaced for DLT assessment.

Table 4. Phase I Dose Escalation and De-Escalation Rules

[figure not shown]
Number of Patients with DLT at a Given Dose Level	Escalation Decision Rule
0 out of 3	Enter 3 additional patients at the next dose level.
1 out of 3	Enter 3 additional patients at the dose level. If no additional DLT enter 3 additional patients at the next dose level.
2 out of 3 or 6	De-escalate the dose to the next lower level and accme 3 patients.
< 2 out of 6 at the highest dose level	This is the recommended phase 2 dose.

Table 5. Phase I Intralesional IL-2 Dosing

	Treatment 1 Dose	Treatment 2 Dose	Treatment 3 Dose	Treatment 4 Dose
Dose Level -1	1×10^6 IU	1×10^6 IU	1×10^6 IU	1×10^6 IU
Dose Level I	3×10^6 IU	3×10^6 IU	3×10^6 IU	3×10^6 IU
Dose Level 2	3×10^6 IU	7×10^6 IU	7×10^6 IU	7×10^6 IU
Dose Level 3	3×10^6 IU	7×10^6 IU	15×10^6 IU	15×10^6 IU

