8.4 All Study Variables

The panel of study endpoints and how they will be measured are described in the below table.

Table 14. Study Variables and Measurements

Endpoint	Variable	Measurement	Comment
Primary- Phase 1	ARR	irRECIST	Objective response at unirradiated sites, the endpoint for measuring responses for the Simon two-stage phase 2 study
Primary- Phase 1	ORR	RECIST and irRECIST	
Primary- Phase 1	DCR	RECIST and irRECIST	
Primary – Phase 1	PFS	RECIST and irRECIST	
Secondary- Phase 1	MTD	CTCAE V4.03	The maximum dose at which <2 of 6 patients experienced a DLT
Secondary- Phase 1	DLT	CTCAE V4.03	Outlined in section 5.4. A DLT is defined as \geq grade 4 injection site reaction OR \geq grade 3 treatment related immunologic adverse event (excluding injection site reactions) OR other \geq grade 3 treatment related adverse events that do not resolve to \leq grade 2 within 14 days of onset during the 30 day DLT period OR Grade 3 diarrhea, AST/ALT $>$ 3 x ULN with bilirubin $>$ 2 X ULN, or pneumonitis that requires holding treatment $>$ 14 days.
Secondary- Phase 2	Safety	CTCAE V4.03	
Translational	PBMC Immunophenotype	FACS	Blood
Translational	PBMC gene expression	qPCR	Blood
Translational	Systemic Cytokine Signature	Luminex	Serum
Translational	Tissue Immune Markers	IHC / IF	Tissue
Translational	Tumor gene expression	qPCR	Tissue
Translational	Mutational load	Whole exome sequencing/ RNA sequencing	Blood and Tissue
Translational	T cell receptor diversity	TCR deep sequencing	Blood and Tissue

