9.0 DATA AND STATISTICAL ANALYSIS PLAN

9.1 Sample Size

This is a phase I/II study that will enroll patients with an advanced solid malignancy, or lymphoma to determine if this regimen converts patients with resistance to PD-1/PD-L1 blockade into responders as determined by abscopal response rate (defined as response rate at lesions not treated with RT + IL-2) using irRECIST as well as ORR, DCR, and PFS using RECIST 1.1.

The phase I dose escalation will employ a standard 3 + 3 design with a goal of determining the MTD through DLT assessment. With three dose escalation levels this arm will recruit up to 18 patients.

The Phase II dose expansion will employ a binomial one stage design which will allow us to evaluate if this therapy can convert those resistant to PD-1/PD-L1 blockade into responders. Response will be assessed according to RECIST and will be evaluated at the non-treatment lesions (abscopal response). In order to minimize the required patient numbers, the 3 patients enrolled at the MTD will be included in the phase II efficacy evaluation. We have chosen a threshold of 5% response as not worthy of further evaluation (p0) and a threshold of 20% as worthy of further evaluation in a larger trial (p1). The trial will enroll a total of 21 patients including the three patients treated at the MTD in the phase I (ntot) and must have greater than 3 responders (rtot) for this regimen to be deemed worthy of further evaluation. This design provides a type I error rate of 0.1 and power of 0.82. This trial design will enroll a total maximum of 25 evaluable patients

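### Table 4 is a bottom-up 3+3 table in a phase I that starts at the top dose: its 0/3 row fails at Level 3 and again after de-escalation, and the fixed count of 3 plus 18 fits only a three-patient MTD cohort

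*Combined protocol and SAP*

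**What the plan says.** Section 5.4.1.1 sets the direction: "We will initiate the trial at Dose level 3 and de-escalate to lower dose levels as needed to establish the MTD". Sections 4.8.5 and 5.2 say the same. Its MTD definition reads: "the highest dose at which no more than one of six patients develops a DLT or Dose Level 3 if the MTD is not reached". Table 14 in section 8.4 words it differently: "The maximum dose at which <2 of 6 patients experienced a DLT".

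Table 4, which 5.4.1.1 presents as the rules to be followed, has four rows:

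- 0 of 3 with a DLT: "Enter 3 additional patients at the next dose level".
- 1 of 3: add three at the same level. "If no additional DLT enter 3 additional patients at the next dose level".
- 2 of 3 or of 6: "De-escalate the dose to the next lower level", and accrue three patients there.
- "< 2 out of 6 at the highest dose level": this is the recommended phase 2 dose.

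On numbers, section 9.1 says that "the 3 patients enrolled at the MTD will be included in the phase II efficacy evaluation" and fixes the efficacy total at 21. Section 2 also gives 21, made up of 18 further patients analysed with those from the MTD. Section 2 allows 3 to 6 patients per level and 6 to 18 in phase I. Sections 1, 2 and 9.1 cap the trial at 25.

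**The concern.** The first two rows of Table 4 assume an untried higher level. In this trial the first cohort is already at the top, and every later cohort sits below a level that has been rejected. The table words its downward step separately, as a move to a lower level, so its plain references to the next level read as upward. A site following the table literally would find no level to go to after 0/3 at Level 3, and would be pointed to a rejected dose after 0/3 at Level 2.

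This table selects the phase II dose, so it should work without anyone having to infer intent. The same uncertainty reaches the efficacy sample: the plan counts three patients at the MTD, while its own MTD definition speaks of six.

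**Working it through.** **1. The plan's own count.** 3 at the MTD + 18 additional = 21, as stated. With six at the MTD, 6 + 18 = 24; holding the total at 21 needs 6 + 15.

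**2. Table 4 against the rest of the plan.**

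| Result | Table 4 | Elsewhere |
|---|---|---|
| 0/3 at Level 3 | Three at the next level; none exists | 5.4.1.1 takes Level 3 forward. The last row of Table 4 and Table 14 speak of six patients; section 2 has a phase I minimum of 6 |
| 1/3, then 0/3, at Level 3 | Second row: next level. Last row: phase 2 dose | MTD by definition (1 of 6) |
| 0/3 at Level 2, Level 3 rejected | Three at the next level, literally Level 3 | The MTD definition needs three more at Level 2 |
| 1/3, then 0/3, at Level 2, Level 3 rejected | Three at the next level, literally Level 3 | MTD by definition (1 of 6) |

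The first and third rows are the open ones. Only the first, with three patients accepted as enough, yields a three-patient MTD cohort under any text in the plan.

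**3. How often each path arises.** The documents give no DLT rate for this combination, so the rates *p* are assumptions. The low end, 2/187 = 1.1%, is the grade 3 rate across the intralesional IL-2 trials in section 4.8.4. Section 4.8.5 adds two pilot patients at Level 3 with no DLT.

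- 0/3: (1−p)³
- 1/3 then 0/3: 3p(1−p)⁵
- Level rejected: one minus the sum of these two

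| p at Level 3 | 0/3 | 1/3 then 0/3 | Rejected |
|---|---|---|---|
| 1.1% | 0.968 | 0.030 | 0.0013 |
| 5% | 0.857 | 0.116 | 0.027 |
| 10% | 0.729 | 0.177 | 0.094 |
| 20% | 0.512 | 0.197 | 0.291 |
| 30% | 0.343 | 0.151 | 0.506 |

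The chance of reaching 0/3 at Level 2 after Level 3 is rejected is (rejected at Level 3) × (1−p₂)³:

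| p₃, p₂ | Calculation | Chance |
|---|---|---|
| 1.1%, 1.1% | 0.0013 × 0.968 | 0.001 |
| 5%, 5% | 0.0266 × 0.857 | 0.023 |
| 10%, 10% | 0.0939 × 0.729 | 0.068 |
| 10%, 5% | 0.0939 × 0.857 | 0.080 |
| 20%, 10% | 0.2914 × 0.729 | 0.212 |
| 30%, 20% | 0.5057 × 0.512 | 0.259 |

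These are chances of meeting the faulty instruction, not of re-treating anyone at Level 3.

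**4. The cap of 25.** A rejected level holds three patients (2 or more DLTs in the first three) or six (1/3, then a further DLT). With one rejected level and the MTD cohort topped up to 21, the total is 3 + 21 = 24 or 6 + 21 = 27. With six at the MTD and 18 added, it is 3 + 6 + 18 = 27 or 6 + 6 + 18 = 30.

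**The case against.** The best defence is that the prose already supplies what the table lacks. The fallback in the MTD definition takes Level 3 forward after 0/3, and 9.1 refers to three patients at the MTD, so the intended path can be inferred: 0/3 at Level 3, accept, expand. This stands as far as the dose goes. A reader might infer that the most likely first result leaves the trial with no dose to carry forward; it does not. What remains is that three patients conflict with the six in Tables 4 and 14 and with the phase I minimum in section 2.

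A reader might also infer that patients will be sent back to a rejected dose. The documents do not support that. Three sections describe de-escalation from Level 3, the MTD definition excludes a level with 2 or more DLTs in six, and Appendix 6 has cohort-expansion minutes going to the DSMC. Nor is 1/6 at Level 2 open, since the definition makes it the MTD; counting it would raise the last two chances in step 3 to 0.264 and 0.358.

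Rates of 20-30% have no source in the documents. The low end may even be generous: one of the two grade 3 events in Table 1 was an injection-site reaction, and grade 3 injection-site reactions are not DLTs under 5.4.1.1.

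Lastly, the efficacy total is fixed at 21 in both section 2 and 9.1; the 18 additional patients appear only in section 2, so topping up to 21 is the natural reading. A reader might still infer that 24 patients would push type I error above 0.1. That needs a cutoff of 3 or more responders (0.116 at n = 24). Section 9.1 prints greater than 3, which gives 0.030. The cutoff of 3 or more does reproduce the stated power at n = 21 (0.821, against 0.630 for the printed rule), but that mismatch is a separate matter and adds no weight here.

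**Conclusion.** The point holds as a fault in a written rule. Table 4 has no usable action for 0/3 at Level 3, and its action for 0/3 at Level 2 after de-escalation is wrong: it should add three patients there. Re-exposure at a rejected dose is unlikely. The chance of reaching the Level 2 cell runs from about 0.001 to 0.26 across the assumed rates, and is at the bottom of that range if the IL-2 experience cited in the plan carries over to this combination.

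The fixed counts of 3 and 18 give 21 only with a three-patient MTD cohort. With six, the plan does not say whether 24 are analysed, enrolment stops at 21, or three of the six are left out. At assumed Level 3 rates of 5-30%, Level 3 passes as 1/6 with chance 0.12 to 0.20, so this does not depend on de-escalation. The correction is cheap and should be made.

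**What to change.** Replace Table 4 with a de-escalation table:

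- 1/3: add three at the same level.
- 2 or more DLTs at a level: go down one level and never re-enter the rejected one.
- 0/3 below Level 3: add three at the same level.
- No more than 1 of 6: this level is the MTD and the phase 2 dose.
- Level -1 not tolerated: halt, as 5.4.1.1 already says.

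For 0/3 at Level 3, state the same choice in 5.4.1.1, Table 4 and Table 14: either three patients suffice, or three more are added. That choice belongs to the investigators. If three suffice, the phase I minimum of 6 in section 2 should change too.

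In 9.1 and section 2, replace the fixed 3 and 18 with all patients treated at the MTD plus enough to reach 21 (18 after a cohort of three, 15 after six).

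Reconcile the cap of 25, because six patients at a rejected level plus 21 makes 27. Either raise it or say which patients it counts.

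The cost is one table and matching edits. Requiring six at Level 3 means up to three more DLT-evaluable patients before expansion; if the level passes, they count toward the 21. It also adds one more path to six at a rejected level (0/3, then 2 or more of the next three), with chance (1−p)³ × [3p²(1−p) + p³]: 0.020 at 10%, 0.053 at 20% and 0.074 at 30%.

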5.4.1.2 Phase II Dose Modification

Figure 6: Phase II Dose Modification Schema of IL-2

Any dose level that is found to be intolerable or associated with grade 3-4 toxicity or intolerable grade 2 AE will be deemed a TLT. TLT = Phase II treatment limiting toxicity.

Table 6. Phase II Intralesional IL-2 dosing (intra-patient dose escalation)

P2 Dose -1	1×10^6 IU
Level 1 (starting dose level)	3×10^6 IU
Level 2 (2nd dose)	7×10^6 IU or Phase I MTD
Level 3 (3rd and 4th dose)	15×10^6 IU or Phase I MTD

Phase II will be conducted using the MTD. For phase II, a treatment limiting toxicity (TLT) will be defined as an IL-2 treatment related grade 3-4 non-hematologic or grade 4 hematologic toxicity and will require dose de-escalation. A TLT must resolve to grade 2 or less before the next de-escalated dose is administered. Treatment intolerance will be measured in phase II to define the percentage of patients that have to come off study treatment or miss an IL-2 treatment due to inability to tolerate the full course of therapy. This is a separate measure from the MTD assessment in phase I and is only measured during phase II. Treatment intolerance will be defined as a TLT that does not resolve to grade 2 or less within 5 days, is not responsive to management, or occurs at the lowest dose level (1 million IU IL-2). In this case the patient will be removed from trial and the therapy will be deemed intolerable for that patient. If a dose of IL-2 is missed due to TLT not resolving to grade 2 or less within 5 days this falls into the definition of treatment intolerance. If a dose IL-2 is missed for other reasons this does not qualify as treatment intolerance. The TLT period begins with the administration of IL-2 and lasts up to 7 days after the last injection of IL-2. As outlined above the initial dose of intralesional IL-2 will be administered as 3 million IU test dose. If there are IL-2 related grade 3-4 non-hematologic or grade 4 hematologic treatment related adverse effects the dose will be de-escalated for the second treatment to 1 million IU. If there are grade 3-4 non-hematologic adverse effects, or grade 4 hematologic adverse effects at the 1 million IU dose the patient will be removed from study and the therapy deemed intolerable. For a given patient dose escalation will occur if there are no IL-2 related grade 3-4 non-hematologic or grade 4 hematologic treatment related toxicities. For each patient if a dose level is associated with grade 3-4 non-hematologic or grade 4 hematologic toxicity this will be deemed a TLT and the patient will be de-escalated to the lower dose for the next treatment. Once the dose is decreased there will be no further dose re-escalation allowed for an individual patient. If a planned dose cannot be delivered within the prescribed week it will be skipped.

Intratumoral IL-2 is well tolerated per Table 1 above with the majority of patients experiencing mild toxicity.

Table 7. Adverse Event Management

Injection site pain	Administer 325-650 mg acetaminophen po every 4-6 hours prn
Flu-like symptoms	Administer 325-650 mg acetaminophen po every 4-6 hours prn
Headache	Administer 325-650 mg acetaminophen po every 4-6 hours prn
Nausea/vomiting	Prescribe antiemetics per treating physician's recommendation
Diarrhea	Prescribe antidiarrheal agents per treating physician's recommendation

Hypotension is a rare event with only 1 patient from the above clinical trials and case series reporting it.

Table 8. Listing of the Blood Pressure Goals

Baseline Systolic Blood Pressure	Target Systolic Blood Pressure on Days of Treatment
<100 mm Hg	>80 mm Hg
100-120 mm Hg	>85 mm Hg
>120 mm Hg	>90 mm Hg

If patient's BP is less than 80 mm Hg on the day of treatment administer 1-1.5 L of fluid to meet the blood pressure goals. If BP remains less than 80 mm Hg, the patient cannot be treated and the dose will be delayed for up to 5 days. This is not considered a DLT or treatment intolerance unless the low BP is due to IL-2 therapy.

If patients experience a clinically significant Grade 3 or greater adverse event please contact the principal investigator to discuss AE management.

